Participants may require out-of-protocol emergency services such as hospitalization or other psychosocial programs. These participants will be retained in the protocol whenever possible. A participant who needs to be hospitalized (e.g., for suicidality) will be reentered into the protocol after hospital discharge if the participant and family agree to continue. Participants will not be withdrawn if they seek ancillary psychosocial treatments outside of the study. We recognize that the availability of adjunctive non-protocol treatments could statistically confound our results, especially if they occur in one treatment condition more than another. This potential threat to internal validity must be balanced against the clinical needs of the adolescent participant, which may not be met by study protocol interventions. As indicated, we will record each participant's non-protocol treatments (e.g., medications received, frequency and type of extra psychotherapy sessions) using a *Treatment Utilization Form*. We will examine in the data analyses whether the adolescents in the two treatment conditions differ in the intensity (e.g., number of non-protocol sessions), costs, or duration of ancillary services or crisis sessions. We will then use these variables as covariates when evaluating the effects of treatment condition on the teen's symptomatic, functional, or family outcome variables. In the primary mentor's prior studies in mood disorders (e.g., [name] et al., 2013), youth at high-risk for bipolar disorder in FFT and Enhanced Care did not differ on the frequency of variables such as undertaking ancillary therapies, emergency room visits, school counseling, or hospitalizations.

Circumstances That May Require Study Withdrawal

Noncompliance. Participants will be withdrawn from the protocol if they are noncompliant with the study procedures (for example, miss 4 consecutive treatment sessions without calling ahead; refuse to participate in follow-up interviews). The circumstances that may require administrative withdrawal will be spelled out in the consent forms.

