Significant symptomatic or functional deterioration. If a participant or family member endorses significant symptomatic or functional deterioration at any point throughout the study protocol or if study staff witness significant deterioration, the participant will be encouraged to seek services with ancillary psychosocial and/or psychopharmacological therapy. Study staff will make every effort to continue to include the participant in the study protocol and participants will be continued in the treatment if they continue to consent to treatment, can tolerate the study protocol, and are not a disturbance to the group setting of the treatment. In cases where the patient requires hospitalization, can no longer tolerate the study protocol, or become a disturbance to the group, the participant will be withdrawn from the study.

Participants will have been informed of these rules during the recruitment phase of the study, both through information given orally and via our informed consent procedures. We will make clear that discontinuing participation in the study will in no way jeopardize their access to other treatments provided by outpatient or inpatient services at the study site. Whenever possible, we will continue to follow these adolescents/YAs using the research outcome battery so that they can be included in intent-to-treat analyses.

Reporting Adverse Events

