treatment, is based on the premise that participants need to practice the skills in order to improve. Since participants commonly forget to do the skills, lose their homework assignments, or feel unmotivated to complete the skills, it challenges treatment developers to improve the current treatments and address these barriers to patient compliance. **We propose using a mobile app to improve patient compliance for youth at risk for SMD.** A mobile app can remind participants of skills they need to practice, provide the psychoeducation and skill-practice within the app, and provide contingencies that reward and increase motivation for skill-practice. Additionally, the large amounts of data that a mobile app collects allows for advanced statistical techniques, such as machine learning, to be applied. These efforts can provide a wide range of benefits to youth at risk for SMD and clinical science more broadly. Improving patient compliance can improve treatment outcomes, which reduces burdens on families who face these psychiatric challenges and society at-large who faces this emotional and financial burden. Additionally, through use of machine learning, we can better determine who will and who is benefitting from a skills-based treatment, like CBT. This prediction can help us better tailor treatment recommendations for patients and determine which patients will or will not benefit from a particular type of treatment.

STATISICAL DESIGN AND POWER

Power calculations

For this pilot RCT, we plan to randomize 60 participants to the randomized controlled-trial of the mobile-enhanced treatment. The two treatment groups will be randomized in a 1:1 ratio. Based on pilot trials of this treatment group as well as my primary mentor's ([name]) previous work with interventions for adolescents at high risk for SMI, we anticipate no more than 15-20% dropout by the end of the six-month study. Thus, we expect a final sample size of about 50 with full follow-up (25 in each treatment condition) across 3 assessment time-points (baseline, post-treatment, and three-month follow-up). Actual power will be higher as our general linear mixed modeling allows inclusion of data from subjects with partial data.

Additionally, data collected via the mobile application (app) should greatly increase the number of measurements.

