The remaining measures for treatment adherence (i.e., Homework Compliance Scale and Psychosocial Compliance Scale), as well as measures for app acceptability (i.e., Subjective App Usability Scale) and treatment acceptability (i.e., Subjective Treatment Acceptability) will be collected at the post-treatment assessment. Maintenance of treatment adherence will also be collected at the 3-month follow-up assessment. Treatments will be compared on these outcome measures using one-way analysis of variance (ANOVA).

- **Secondary analyses:** Treatment conditions will be compared using a general linear mixed modeling (GLMM) approach for secondary outcome variables (i.e., psychiatric functioning and psychosocial functioning) using IBM SPSS software. Time will be based on the standard interval assessments of the study – the baseline, post-treatment, and follow-up assessment). Time, treatment condition, and their interaction will be the primary predictors (controlling for any significant covariates). Psychiatric symptoms, psychosocial functioning, and emotion regulation (measured continuously) will be the outcome variables for these analyses.

We will also test a mediation analysis, with average participant adherence (measured throughout the study) as the mediator between treatment conditions and the secondary outcome variables. This will be done in two sets of analyses using the SPSS Process macros, which is a statistical package within SPSS that runs bootstrapped mediation analyses. First, the effect of treatment condition, mediated by average treatment adherence, on post-treatment psychiatric and psychosocial functioning will be examined. Second, the effect of treatment condition, mediated by average treatment adherence, on 3-month follow-up psychiatric and psychosocial functioning will be examined.

- **Exploratory analyses:** Two exploratory analyses will be examined. We will make use of the app's big data collection to begin to elucidate the app's effect on participant adherence and clinical outcomes.

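### The mediation is planned in SPSS PROCESS with no method for missing outcomes, so a default run drops youths with recorded adherence, loses power, and may bias the indirect effect in a direction the documents do not fix

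*Combined protocol and SAP*

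**What the plan says.** All references are to the combined protocol and SAP.

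- **Statistical analyses, Aim 2, Secondary analyses.** Average adherence, measured throughout the study, is the mediator between treatment condition and psychiatric and psychosocial functioning. On software the plan says: "This will be done in two sets of analyses using the SPSS Process macros". One set uses the post-treatment outcome and the other the 3-month outcome, both bootstrapped. The section does not say who is included, how a missing outcome is handled, or how adherence is averaged for a youth who stops early.
- **Aim 2, Primary analyses.** Adherence is measured weekly and compared between conditions by mixed model.
- **Power calculations.** On size and allocation: "we plan to randomize 60 participants to the randomized controlled-trial of the mobile-enhanced treatment" and "The two treatment groups will be randomized in a 1:1 ratio". On loss: "we anticipate no more than 15-20% dropout by the end of the six-month study". On what remains: "we expect a final sample size of about 50 with full follow-up (25 in each treatment condition"). On partial data: "Actual power will be higher as our general linear mixed modeling allows inclusion of data from subjects with partial data". That last sentence concerns the mixed models only.
- **Circumstances That May Require Study Withdrawal, Noncompliance.** The examples of noncompliance that lead to withdrawal are: "miss 4 consecutive treatment sessions without calling ahead; refuse to participate in follow-up interviews".
- **Same heading, closing paragraph on deterioration.** Youths who leave the protocol are to be followed with the outcome battery where possible, "so that they can be included in intent-to-treat analyses".

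**The concern.** Mediation needs two equations: adherence on condition (path a), and outcome on condition and adherence (path b). Only the second needs the outcome. Under listwise deletion, a youth with no outcome at the visit is removed from both, so path a is estimated without youths whose condition is known and whose adherence was at least partly recorded.

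Two things are at stake. The first is precision, because recorded mediator data are thrown away in a small trial. The second is validity. Noncompliance is a named ground for leaving, so missing outcomes may be related to the mediator, and path a would then describe the youths who were assessed and not those randomised. The mediation tests the trial's rationale that better compliance is what improves outcome. It is also the one Aim 2 comparison of outcomes over follow-up to which the plan's reassurance about partial data does not extend.

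**Working it through.** **Inputs from the documents.** 60 randomised 1:1; 15-20% dropout by six months; about 50 with full follow-up, 25 per arm; two-sided alpha .05; effect size f = .30, which the plan gives for the group-by-time interaction.

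**Assumed, because the documents give no values.** Path a = 0.6 SD (f = .30 read as a two-group difference, d = 2f = 0.6); path b = 0.5 SD; no direct effect; and the dropout mechanisms named below. The mediator is taken to be the weekly adherence record.

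**1. The plan's own figure.** Completers = 60 × (1 − d): 60 × 0.85 = 51; 60 × 0.833 = 50; 60 × 0.80 = 48. The stated figure of about 50 reproduces. A complete-case 3-month mediation would omit 60 − 51 = 9 to 60 − 48 = 12 randomised youths.

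**2. Power when dropout is random.** Path a alone is a two-sample comparison at d = 0.6. Power is 54.7% with 50 youths and 62.8% with 60, a gap of about 8 points. Requiring both paths to be significant, with b always from complete cases, simulated trials of 60 with one sixth missing give:

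| Path a estimated in | Joint power over repeated runs |
|---|---|
| complete cases | 51-54% |
| all 60 | 59-61% |

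The difference is about 7 to 8 points with no bias at all. If the odds of dropout triple per SD lower adherence under one rule for both arms, it is 47% against 60%.

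**3. Bias of the indirect effect.** The quantity is (a × b among completers) / (a × b among all randomised), from large simulations with M = 0.6·T + e and Y = 0.5·M + error, and one sixth missing.

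| Odds ratio of dropout per SD lower adherence | One rule for both arms | Same dropout rate forced in each arm |
|---|---|---|
| 1 | 1.00 | 1.00 |
| 2 | 0.95 | about 1.00 |
| 3 | 0.89 | about 1.00 |
| 4 | 0.85-0.86 | about 1.00 |

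At 20% missing, the common-rule ratios for odds ratios 2, 3 and 4 are 0.94, 0.88 and 0.84. The limiting case, in which the least adherent sixth are exactly those missing, gives 0.64. Path b stays at 0.50 in all of these, so the whole change is in path a. That follows from making dropout depend on adherence alone; dropout that depends on the outcome would alter b as well.

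The common rule attenuates because it removes more control youths: at odds ratio 3, about 20% of controls against 13% of the app arm, or 30 × 0.80 = 24 and 30 × 0.87 = 26 completers.

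**4. The opposite direction.** With b = 0.4 and a = 0.3, 0.5 or 0.8, losing the lowest adherers at 20% in the app arm and 10% in control gives ratios of 1.53, 1.32 and 1.19. Losing low adherers only from the app arm, with random loss in control, gives 2.01, 1.60 and 1.37.

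**5. Continued assessment.** If half of the youths below a common adherence cut-off are still assessed, the limiting 0.64 rises to 0.86-0.87.

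**The case against.** A reader might infer that the indirect effect is biased toward zero, because noncompliant youths are withdrawn and a working app would leave more of them in the control arm. The documents do not support a fixed direction. They give no dropout by arm or reason, and the only expectation by arm is equal loss, 25 completers in each. With adherence-dependent but equal loss the ratio is about 1.00, and it exceeds 1 if low adherers leave the app arm more. This objection stands. It does not remove the problem, since 24 and 26 completers would look close to the planned 25 and 25 while the ratio was 0.89.

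Withdrawal is also not the same as a missing outcome. Withdrawn youths are to be assessed where possible, and the noncompliance examples concern unannounced missed sessions and refused interviews. The exploratory analyses list the components of adherence as skill-practice, symptom monitoring and review of session content. Selection on the mediator is therefore smaller and indirect. This also stands, but refusing interviews does mean a missing outcome, and the plan still budgets for about 50 of 60.

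The size needs qualifying in three ways. The 15-20% applies at six months; at 5-10% missing, which may suit post-treatment better, the common-rule ratio at odds ratio 3 is 0.95-0.92. The 0.64 is a bound. The power figures use joint significance as a stand-in for the planned bootstrap.

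Finally, the effect of the app on adherence is tested in the primary mixed model, where partial data are allowed, and the plan disclaims formal efficacy and effect-size estimation. So the main adherence conclusion does not rest on PROCESS. The mediation is nevertheless a committed analysis. That it would give one path-a estimate per visit is an ordinary result of two analysis sets and not an error in itself.

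**Conclusion.** The concern holds as a gap in method with a definite cost and a possible bias. A default PROCESS run would leave out the 9 to 12 of 60 youths expected to lack full follow-up, including from an equation that does not need their outcome. The loss of about 7 to 8 points of joint power does not depend on any dropout mechanism, given paths of 0.6 and 0.5 SD. The bias does depend on it: about 0.85-0.95 of the true indirect effect under one adherence-related rule common to both arms at odds ratios of 2 to 4, about none with equal loss by arm, and inflation if the app arm loses more low adherers. Planned assessment after withdrawal reduces the loss without removing it. The path sizes and dropout mechanisms are assumptions, and complete-case deletion is the software's default, not something the plan states. Because the direction cannot be known in advance, the method should be fixed before the data are seen. This should be changed, but it does not threaten the primary analysis.

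**What to change.** In the Aim 2 secondary analyses:

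1. State that the mediation includes all randomised youths.
2. Name one method. Either fit both equations as a single path model by full-information maximum likelihood with bootstrap intervals, or multiply impute the missing post-treatment and 3-month outcomes from condition, weekly adherence, baseline outcome and any earlier outcome, and run the mediation in each imputed set.
3. Define average adherence over the full planned period, with a stated rule for weeks after early stopping. Averaging only the weeks before dropout could overstate early leavers' adherence and itself bias path a.
4. Report complete-case PROCESS as a sensitivity analysis, with dropout by arm.

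The cost is SAP wording and modest extra analysis, with no new data or participants. The downside is reliance on outcomes being missing at random given recorded adherence and the other variables in the model.
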